A non-surgical treatment option for the management of osteoarthritis include injectables such as corticosteroids and platelet rich plasma (PRP). These injectables work by positively affecting cartilage cells, also known as chondrocytes, and the cells of the joint lining tissue, also known as synoviocytes. PRP is an autologous derived blood product, i.e. a joint injectable made from the patient's own blood at the time and location of injection with simple blood centrifugation. Studies in the bench-top laboratory setting have provided in-vitro evidence that PRP decreases synoviocyte production of metalloproteinases, an inflammatory protein with negative effects on cartilage, decreases the effects of inflammatory proteins such as IL-6 on chondrocytes, and has an anti-inflammatory effect upon the gene expression of chondrocytes and synoviocytes[14-16]. While these are mechanisms that can help manage osteoarthritis after it arises, they also are mechanisms that could help prevent osteoarthritis before it forms. Recent comparative studies of PRP to other injectables in the management of osteoarthritis suggest a greater, long-lasting effect of PRP than other injectables [1-6].

Orthopedic research has focused on methods to prevent PTOA after ACL injury. Recent study involving the post-injury ACL joint milieu suggested that an early intervention of joint aspiration and corticosteroid injection has positive effects, including a decrease in biomarkers responsible for chondral degeneration [13]. This combined with in vitro study on the effects of PRP on chondrocyte and synoviocyte activity suggest that PRP has potential to affect the ACL-injured joint. However, current literature is lacking in regard to this assertion, and in vivo study of PRP to positively affect the joint after following ACL injury is warranted.

2 Objectives

The main objective of this study is to determine if an early intervention of joint aspiration and PRP injection will positively affect the biomarkers representative of chondral degeneration in patients with ACL injuries. We hypothesize that the intervention will reduce the volume of inflammatory and chondrodegenerative biomarkers following ACL injury.

3 Participant Eligibility

Inclusion Criteria: Patients between the ages of 14 and 40 years with closed growth plates as visualized on plain radiography, no history of previous traumatic ipsilateral knee injury, and no

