Effect of Platelet Rich Plasma Injections on Inflammatory and Chondrodegenerative Biomarkers in Patients with Acute Anterior Cruciate Ligament Tears

[name].

Page 3 of 7

clinical evidence of posterior cruciate ligament injury with no more than grade 1 medial or lateral collateral ligament injury.

Exclusion criteria: Patients without a palpable knee effusion, an injury occurring more than 10 days before enrollment, previous ipsilateral knee surgery, intra-articular cortisone or PRP injection into either knee within 3 months of injury, participation in another clinical drug trial within the 4 weeks before injury, and a history of any inflammatory disease or immune-comprised. Any patient who will have difficulty obtaining internet access, does not have an active e-mail address, or is unable to comprehend study documents or give informed consent will be excluded.

4 Participant Enrollment

60 patients will be recruited through the Andrews Institute physician practices. Potential participants will be prescreened for inclusion and exclusion criteria through standard of care medical evaluations. Once a potential participant has agreed to be involved in the study, they will go through the described informed consent process. Patients meeting the inclusion criteria will have the study explained to them by one of the members of the investigating team, and they will be given an opportunity to participate if they are interested. No specific advertising or recruitment material will be utilized.

The participants will then be randomly placed in one of the two study groups and be scheduled to receive either an injection of PRP or no injection in their involved knee.

Participants will not be billed for the joint aspirations or PRP injections.

5 Study Design and Procedures

Study design will be randomized control trial. Participants who meet the inclusion criteria will have the study explained in detail and informed consent will be obtained as outlined above.

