Patients will be randomized to 1 of 2 groups. Both groups will have joint aspirations performed at an initial visit, within the first 10 days after injury, and at the time of surgery, within 4 weeks of injury. Group 1 will receive only joint aspirations as outlined above. Group 2 will undergo aspirations as outlined above and also receive a PRP injection at the initial visit and at a second visit 5-12 days after the initial visit. Joint aspirations and injections will be performed through the superolateral, suprapatellar approach. Patients will be instructed not to take any prescription or over-the-counter nonsteroidal anti-inflammatory medications. Patients will be encouraged to rest, ice, and elevate their injured knee.

Effect of Platelet Rich Plasma Injections on Inflammatory and Chondrodegenerative Biomarkers in Patients with Acute Anterior Cruciate Ligament Tears

[name].

Page 4 of 7

PRP Manufacturing: PRP preparation will involve Autologous Conditioned Plasma disposables (Arthrex, Naples, FL, USA), a commercially available kit for the production of PRP.

Preparation will follow the manufacturer's instructions. The treating physician will then inject the PRP into the involved knee joint following standard aseptic technique per the physician's standard of care. This entire process will be completed in a single patient visit. A 0.1-0.5 mL sample of the PRP will be inserted into a vacutainer for analysis of cell count. Any unused portion of a sample in the physician's office will be disposed of through standard biohazard waste disposal systems as required by law.

Biomarker Analysis: Samples will be prepared and frozen at -80° C until all study sample have been obtained. Enzyme-linked immunosorbent assay kits will be used to assess chondrodegenerative & synovial fluid biomarkers.

6 Expected Risks and Benefits

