A power analysis was performed to determine sample size based upon recent clinical trials. Analysis utilized the average of standard deviation to detect average of group mean effect at 80% power. This determined that 25 patients per group would be needed to reach statistical significance. 10 additional patients will be account for potential patient withdrawal or lost-to-follow-up.

Ranges, means and standard deviations for all measures will be determined and calculated. Data will be analyzed for differences between groups using a t-test design, using a significant p-value of < 0.05 for rejecting the null hypothesis.

10 Quality Control and Assurance

All protocols will be monitored and analyzed data will be checked for accuracy by the principal investigator and /or a designated AREF research team member. All medical data will be kept in compliance with HIPAA guidelines.

11 Regulatory Requirements

Informed Consent:

The informed consent process will be performed by one of the study investigators or staff, in the office. All participants will have the study described to them and will give as much time as they require to read an approved, stamped version of the informed consent document. After signing of the informed consent document, participants will be given a copy for their records. This process will take place only after the patient has consented to proceed with the study.

Participant Confidentiality:

Participant confidentiality information is listed above in #7 (Data Management Procedures). All medical data will be recorded and stored in compliance with HIPAA guidelines.

12 References

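### The initial-visit biomarker value has no stated role in the between-group t-test; a prespecified ANCOVA would use it at almost no cost

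*Combined protocol and SAP*

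**What the plan says.** Section 5 (Study Design and Procedures) provides two samples per patient: "Both groups will have joint aspirations performed at an initial visit, within the first 10 days after injury, and at the time of surgery". In the treated arm, "Group 2 will undergo aspirations as outlined above and also receive a PRP injection at the initial visit", with a second injection 5 to 12 days later. The first aspirate is therefore a natural baseline, although the order of aspiration and injection within that visit is implied and not stated.

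Section 9 (Statistical Considerations) says that "Data will be analyzed for differences between groups using a t-test design", with p below 0.05 as the criterion. It names no time point, change score or covariate, and no other section does so.

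On sample size, section 9 says "Analysis utilized the average of standard deviation to detect average of group mean effect at 80% power" and that "25 patients per group would be needed to reach statistical significance"; ten more are added for losses. Section 4 agrees that "60 patients will be recruited".

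Section 2 sets out to learn whether "an early intervention of joint aspiration and PRP injection will positively affect the biomarkers representative of chondral degeneration", and hypothesises that "the intervention will reduce the volume of inflammatory and chondrodegenerative biomarkers following ACL injury". That wording fits either a lower value at surgery or a larger fall from the initial visit.

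**The concern.** The section 9 sentence can be read as two different analyses. A t-test on surgery values ignores the initial sample. A t-test on the change subtracts it with a fixed weight of 1, which adds noise when the two measurements are weakly correlated or the initial value is the more variable. Which test is better depends on a correlation and an SD ratio that the documents do not give.

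Two things are at stake. The first is power: a plan sized for 80% could be analysed by a method with far less, or could leave available precision unused. The second is the open choice itself: if the decision were made after seeing results, the nominal 5% would no longer hold. ANCOVA estimates the weight from the data, so neither unknown has to be guessed.

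**Working it through.** **Inputs.** From section 9: 25 per group, 80% power, p < 0.05. From section 4: 60 recruited, and 2 × 25 + 10 = 60 agrees. Assumed, because not stated: two-sided test, equal allocation, normally distributed outcome, correlation r between initial and surgery values from 0 to 0.7, and ratio k = initial SD / surgery SD of 0.5, 1 or 1.5.

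**Step 1: the plan's own figure.** No difference or SD is given, so 25 per group cannot be reproduced, only back-solved.
- Normal approximation: d = (1.960 + 0.842) × √(2/25) = 0.792.
- Noncentral t with 48 df: 80% power requires d = 0.8087, used below.

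**Step 2: change-score t-test.** Randomisation makes the expected initial values equal, so the mean difference is the same as at surgery. In units of the surgery variance, the change has variance 1 + k² − 2rk. The standardised effect is d / √(1 + k² − 2rk), with 48 df. Example, k = 1, r = 0.3: 0.8087 / √1.4 = 0.683, power 65.8%. The change score is worse than the surgery value alone when k² − 2rk > 0, that is when r < k/2 (0.5 only if the SDs are equal).

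**Step 3: ANCOVA.** With N = 50 and the slope estimated, the effect is d / √((1 − r²)(1 + 1/(N − 4))), with N − 3 = 47 df.
- r = 0: 0.8087 / √(47/46) = 0.800, power 79.1%.
- r = 0.5: 0.8087 / √(0.75 × 47/46) = 0.924, power 89.2%.

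**Step 4: power (%) at 25 per group.**

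| Correlation r | 0 | 0.1 | 0.2 | 0.3 | 0.5 | 0.7 |
|---|---|---|---|---|---|---|
| t-test, surgery value | 80 | 80 | 80 | 80 | 80 | 80 |
| t-test, change, k = 0.5 | 70.7 | 74.3 | 78.1 | 82.0 | 89.9 | 96.5 |
| t-test, change, k = 1 | 50.8 | 55.1 | 60.1 | 65.8 | 80.0 | 95.1 |
| t-test, change, k = 1.5 | 34.2 | 37.1 | 40.6 | 44.7 | 56.3 | 74.3 |
| ANCOVA | 79.1 | 79.5 | 80.7 | 82.7 | 89.2 | 97.2 |

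Simulation with a fitted slope (40,000 runs) gave 79.4, 79.6, 80.9, 82.7, 89.4 and 97.4 for ANCOVA. The change score is at its best when r = k, where the fixed weight happens to be optimal; at r = k = 0.5 it leads ANCOVA by only 0.7 points.

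**Step 5: break-even and full recruitment.** ANCOVA passes the surgery-value t-test at r of about 0.15. If all 60 patients are evaluable (30 per arm), the surgery-value t-test has 86.9%, ANCOVA has 86.3, 86.6, 87.6, 89.2, 94.1 and 99.0%, and break-even is about 0.135.

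**Step 6: error rate if either t-test may be reported.** Null simulation, 25 per arm, 100,000 runs: 8.4% to 9.3% at k = 1, 7.1% to 7.3% at k = 0.5, and 9.2% to 9.9% at k = 1.5. ANCOVA alone: 4.9% to 5.1%.

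**Step 7: missing initial values.** With 2 of 25 initial values per arm missing at random and replaced by the pooled mean, the null rate is 4.9% to 5.0%. Power is 79.5, 79.6, 80.8, 82.4, 88.6 and 96.2%, at most about 1 point below the complete-data simulation.

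**The case against.** The strongest reply is that nothing is broken. In a randomised trial an unadjusted comparison is valid, and the plainest reading of the sentence is a t-test on surgery values, which keeps the planned 80% at every correlation. The low change-score powers belong to an analysis the plan never names, and the inflated error rate to selective reporting it never proposes. The gain from ANCOVA depends on an undocumented correlation between a sample taken up to 10 days after injury and one taken up to 4 weeks after. At r = 0.2 the gain is about 1 point, at 0.3 about 3. All of this stands, and it limits the point to efficiency and an unfixed choice. It does not show that leaving the choice open is harmless, or that ANCOVA costs anything material.

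A second reply is that biomarkers may be skewed, in which case scale could matter more than the covariate. Distribution is an assumption either way. In lognormal simulations with log-SD 1.0, r = 0.3 and the same effect on the log scale, power was 61.5% for the raw t-test, 62.8% for raw ANCOVA and 82.8% for log-scale ANCOVA. The absolute powers in the table therefore need roughly normal data. The comparison survives: raw ANCOVA stayed within about 1 point of the better t-test, and under the null with log-SD 1 it rejected in 3.8% to 4.3% of runs against 3.9% to 4.1% for the t-test.

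Third, several biomarkers are tested and none is primary. Five independent tests at 5% would give 1 − 0.95⁵, about 23%. ANCOVA does not address this; it is a separate issue.

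**Conclusion.** The point holds as a recommended improvement, not as an error that invalidates the trial or the figure of 25 per group. The plan collects a baseline for each patient, gives it no role, and leaves open which of two t-tests will be run.

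Assuming two-sided 5%, normal data and an effect of about 0.81 SD, that choice moves power between 34% and 97% over the range examined. ANCOVA has 79% to 97%. Against the surgery-value t-test it loses at most 0.9 points (at zero correlation) and gains 9 points at r = 0.5 and 17 at r = 0.7. Confidence in the benefit is moderate, because its size depends on a correlation the documents do not supply.

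**What to change.** Replace the t-test sentence in section 9 with text such as:

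> Each biomarker at the surgery aspiration will be compared between groups by ANCOVA, with group as factor and the same biomarker at the initial aspiration as covariate; the group difference will be given with a 95% CI. A missing initial value will be replaced by the mean of the observed initial values, both groups pooled, so that no patient with a surgery value is dropped.

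The sponsor should confirm that the initial sample is drawn before the first injection, as sections 2 and 5 imply. A log scale is optional; if used, it should be fixed before the assays are run. Missing surgery values and the number of biomarkers tested need separate provisions.

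The cost is two sentences, one degree of freedom, and about 1 point of power if the correlation is near zero. No samples, visits or patients are added. Section 5 keeps samples frozen until collection is complete, so the text can be settled before any assay result exists. Because section 8 foresees data review at intervals, it should be dated before the first assay.

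### Section 9 applies one p < 0.05 t-test rule to a hypothesis about several biomarkers, without naming the primary biomarker, endpoint form, sidedness or number of significant results needed

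*Combined protocol and SAP*

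**What the plan says.** Section 2 (Objectives) sets the main objective as whether aspiration plus PRP "will positively affect the biomarkers representative of chondral degeneration in patients with ACL injuries". The hypothesis is wider: "We hypothesize that the intervention will reduce the volume of inflammatory and chondrodegenerative biomarkers following ACL injury". Both are plural, and the second spans two classes.

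Section 5 (Study Design and Procedures) provides two measurement times: "Both groups will have joint aspirations performed at an initial visit, within the first 10 days after injury, and at the time of surgery". The PRP group will also "receive a PRP injection at the initial visit and at a second visit 5-12 days after the initial visit". The assays are described only by type: "Enzyme-linked immunosorbent assay kits will be used to assess chondrodegenerative & synovial fluid biomarkers". None is listed. Samples stay frozen until collection is complete.

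Section 8 (Data Analysis) has the investigators meeting from time to time to look at and analyse the data, with no schedule and no limit on what is examined.

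Section 9 (Statistical Considerations) gives the whole inferential plan: "Data will be analyzed for differences between groups using a t-test design", "using a significant p-value of < 0.05 for rejecting the null hypothesis". The sample size is 25 per group plus 10 for losses, justified thus: "Analysis utilized the average of standard deviation to detect average of group mean effect at 80% power". No biomarker, difference or SD is given.

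**The concern.** Section 9 speaks of the null hypothesis in the singular, while Section 2 implies at least one null per biomarker. The text is compatible with at least four rules for concluding that PRP reduces the biomarkers:

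- (a) any one biomarker significant;
- (b) any one chondral biomarker significant;
- (c) at least one significant in each class;
- (d) all significant.

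It is also compatible with testing the surgery value or the change from the initial aspirate, and with a one- or two-sided test. These options have very different false-positive rates, and nothing in the plan prevents the choice from following the results. At stake is a false claim that PRP lowers these biomarkers, which is a biomarker claim and not one of patient benefit. If the most favourable biomarker were then emphasised, its estimated effect would also tend to be too large.

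**Working it through.** **Step 1: the plan's own figure.** No difference or SD is given, so 25 per group can only be solved backwards. With n = 2(z₁₋α/₂ + z₁₋β)²/d², two-sided α = 0.05 and 80% power:

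- d = (1.960 + 0.842) × √(2/25) = 0.79. The exact t calculation gives 0.81.
- One-sided: d = (1.645 + 0.842) × √(2/25) = 0.70, or 0.71 by t.
- Total: 2 × 25 + 10 = 60, which agrees with Section 4.

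So 25 per group fits a single unadjusted test of a large effect. It shows no allowance for several biomarkers and does not identify the biomarker.

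**Step 2: false-positive rate by success rule.** From the documents: 25 per group, t-test, 0.05. Assumed, because not stated: two-sided tests; k = 2, 5 or 10 biomarkers, split 1+1, 2+3 or 5+5 between the classes; equal correlation ρ from 0 to 0.8; normal data; no true effect. Rates are for a significant reduction (nominal 2.5%), from simulation with at least 200,000 trials per cell.

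| Rule | k = 2 | k = 5 | k = 10 |
|---|---|---|---|
| (a) any one, ρ = 0 / 0.5 / 0.8 | 5.0 / 4.5 / 3.9% | 11.9 / 9.2 / 6.3% | 22.2 / 14.6 / 8.7% |
| (b) any one chondral (class size 1; 2 to 3; 5) | 2.5% | 3.8-7.3% | 6.3-11.9% |
| (c) one in each class, ρ = 0 / 0.5 / 0.8 | 0.1 / 0.4 / 1.0% | 0.4 / 1.7 / 2.4% | 1.4 / 3.9 / 4.1% |
| (d) all | at most 1.0% | at most 0.4% | at most 0.2% |

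Analytic check of (a) at ρ = 0: 1 − 0.975ᵏ = 4.9%, 11.9%, 22.4%.

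Rule (c) stays below 2.5% for 1+1 and 2+3, but reaches about 4% for 5+5 once the correlation is 0.5 or more.

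**Step 3: sidedness.** If the tests are one-sided, the nominal rate is 5%. Under rule (a) at ρ = 0 it becomes 1 − 0.95ᵏ = 9.8%, 22.6%, 40.1%. At ρ = 0.8, simulation gives about 7.5%, 11.8% and 15.4%. The ranges are therefore about 8-10%, 12-23% and 15-40%.

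**Step 4: endpoint form, one biomarker only.** If the surgery value or the change is reported, whichever is significant, the 2.5% becomes 4.1%, 4.4%, 4.5% and 4.7% at initial-surgery correlation r = 0, 0.3, 0.5 and 0.7. This was computed separately from Step 2, and the two were not combined.

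**Step 5: power of the endpoint forms at 0.81 SD, 25 per group.**

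| r | Surgery value | Change | ANCOVA |
|---|---|---|---|
| 0 | 80% | 51% | 79% |
| 0.3 | 80% | 66% | 83% |
| 0.5 | 80% | 80% | 89% |
| 0.7 | 80% | 95% | 97% |

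**The case against.** The strongest reply is that every figure in Step 2 rests on assumptions. The documents give no k, class split, correlation, sidedness or success rule. With two biomarkers rule (a) gives only 4-5%, and rule (d) is always conservative. This stands: the size is a range, and the upper ends need many uncorrelated biomarkers and the any-one rule together.

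A reader might infer that the trial's false-positive rate is 22%, or 40% one-sided. The documents do not support that, because they do not adopt rule (a) or any other. A reader might also infer that the sponsor decided against multiplicity control, but Section 9 is silent rather than opposed. Nor does Section 8 establish repeated significance testing of the biomarkers. It sets no interim tests, and samples remain frozen until collection ends. What Section 8 does is leave open when choices are made relative to results.

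It can also be said that this is a small exploratory biomarker study. The plan does not say so: it states a hypothesis, a power calculation and a rejection rule. If exploration is the intention, saying so would resolve the point.

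Finally, the main objective narrows the family to chondral biomarkers. That helps, but it names a class, not a biomarker. Part of the protocol's opening text was not available for this review, but Sections 2, 5 and 9, where such a definition belongs, were, and contain none.

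**Conclusion.** The concern holds as a gap in specification that permits inflation, not as proof of inflation. Section 9's single rule cannot be applied to Section 2's hypothesis without choices that the plan leaves open.

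The consequence depends on the choice made. It ranges from no inflation when all biomarkers are required, through about 4% when one per class is required with 5+5 correlated biomarkers, to 4-22% when any one suffices (two-sided, nominal 2.5%). Even a single biomarker has a rate of about 4-5% if its endpoint form is picked afterwards. That last result does not depend on k, though it does assume two-sided testing and r between 0 and 0.7. The plan should be changed. The missing number of biomarkers limits confidence in the size, not in the gap.

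**What to change.** Before any sample is assayed or unblinded data are examined, amend Section 9 to:

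1. State the sidedness and name one primary biomarker, most naturally from the chondral-degeneration class that Section 2 makes the main objective.
2. Compare its surgery-aspirate value between groups by ANCOVA adjusted for the initial-aspirate value, provided that aspirate is drawn before the first injection. Both occur at the same visit and the order is not stated explicitly, so the plan should state it. Otherwise compare the surgery value alone.
3. Report the other biomarkers with Holm adjustment, tested only if the primary is significant, or as exploratory estimates with 95% CIs.
4. Restate the difference, SD and power of 25 per group for the chosen primary.

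Two alternatives are equally acceptable: one co-primary per class with both required, which fits the two-class hypothesis more closely; or declaring the whole study exploratory, with no confirmatory claim. The frozen samples allow any of these to be fixed blind to results if no assay has been run. The documents do not say whether any has.

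Cost: a short rewrite and a sample-size recheck. No extra procedures are needed, as both aspirates are already collected. The downsides are:

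- Non-primary biomarkers lose unadjusted significance claims. At 0.81 SD, the first Holm step at 0.05/(k − 1) has about 61% power for k = 5 and 49% for k = 10, against 80% unadjusted.
- Co-primaries have about 64-73% power if both effects are 0.81 SD (correlation 0 to 0.8).
- The restated power may fall below 80%. Two-sided and unadjusted, 25 per group gives 55%, 68% or 88% at an assumed 0.6, 0.7 or 0.9 SD.
- ANCOVA costs about one point of power if the initial and surgery values are uncorrelated.
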